#### 4.4 Selection of Clinical Sites

UCSF performs approximately 130-140 adult liver transplants for chronic liver disease each year and has had outstanding outcomes based on SRTR data. At the time of protocol design, the median calculated MELD score at transplant is 19.3 (Washburn, 2009) such that approximately 65% would have been eligible based on a calculated MELD score of ≤25 at the time of transplant. However, multiple changes in US liver allocation policy has substantially changed the landscape of liver transplantation. Moreover, throughout the country, the median MELD score at transplant has increased significantly. At UCSF, nearly all subjects who undergo deceased donor liver transplantation across all blood groups with a laboratory MELD score of ≤25 are those who have been granted MELD exception points. The vast majority of these are candidates with HCC which has, historically, accounted for approximately 30-35% of the annual deceased donor liver transplant volume. Exclusion of candidates with active HCV in conjunction with HCC leaves approximately 15% or 20-22 recipients eligible for trial participation annually. Because this trial has additional eligibility assessment steps after enrollment, including donor eligibility for use of cells for a cellular product, we anticipate some attrition at each phase. Therefore, we aim to enroll a minimum of 6-8 patients per year to ensure that 4-5 will progress to darTreg infusion. The pace of enrollment was on par with this plan until October 2015, when the "Wait and Cap" allocation policy for HCC was implemented. The aim of this policy change is to better equalize waitlist mortality of patients with and without HCC. Since the HCC MELD exception score is now capped at 34 and donor livers are regionally shared for candidates with MELD scores ≥35, HCC candidates in Region 5 (UCSF), a region notorious for transplanting at high MELD scores, have much reduced access to transplantation. Our partnership with large transplant centers outside of our region is therefore critical to achieve the enrollment goals for this trial. The UCSF investigators have selected to partner with Mayo Clinic Rochester, Rochester, Minnesota and Northwestern Memorial Hospital, Chicago, Illinois, for many reasons. Mayo Clinic Rochester and Northwestern perform approximately 75-80 and 80-95, respectively, adult liver transplants for chronic liver disease on an annual basis. Both centers are located in United Network for Organ Sharing Region 7 while UCSF is located in Region 5. These two regions differ significantly in the MELD score required to access a deceased donor organ. The lower disease severity at Mayo Clinic Rochester will increase the proportion of transplant recipients eligible to participate in this trial.

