# 10. Study Visits

# 10.1 Stage 1: Screening, Enrollment and PBMC Collection

The first stage of the study encompasses screening A and enrollment. Participants will be selected from the liver transplant waiting lists according to the study eligibility criteria (Screen A). The research study will be explained in lay terms to each potential research participant by the site PI or designee listed on FDA form 1572. The potential participant will sign an informed consent form before undergoing any screening or study procedures. Surrogate consent will not be permitted. Once the informed consent form has been signed, the participant will be assigned a unique participant number. All screening procedures will be completed to ensure that the subject meets inclusion criteria and exclusion criteria A (Section 4.2 and 4.3.1).

Eligible and consented participants enrolled in Cohort 2, 3, or 4 will undergo leukapheresis (or blood draw option for Cohort 2) at any time prior to transplantation to isolate PBMCs, which will be cryopreserved for subsequent Treg purification and expansion. Participants who have detectable HBV DNA at the time of PBMC collection will be terminated from the trial. At the time of transplantation, donor material for these participants will be collected to make donor sBcs and banked to support future expansion of darTregs.

At the time of transplantation, participants will receive Solumedrol, 500 mg intravenously. Within 24 hours after transplantation, participants will be started on MMF in the form of either Cellcept 500mg bid intravenously or orally or Myfortic 360 mg bid by mouth. Within 72 hours after transplantation, participants will be prescribed tacrolimus to target 12-hour trough levels of  $6-8~\mu g/L$ . Please refer to *Appendix 1. Recipient Schedule of Events (Stages 1 and 2)*. Note that collection of AEs and SAEs in Stage 1 are limited to events occurring within 72 hours after leukapheresis.

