### 15.4.1 Analysis Samples

The Safety Sample will be comprised of all study subjects who are consented and receive any study therapy, including leukapheresis, T cell depletion followed by TAC- or EVR-based Treg-supportive IS and darTreg infusion. This excludes consented subjects who were terminated before receiving any study treatment.

Safety and clinical outcomes will be analyzed within the Safety Sample as a whole and within the following two treatment-related analysis periods during which:

- Subjects receive any Thymoglobulin°, followed by TAC- or EVR-based darTreg supportive IS
- Subjects receive darTreg infusions at any dose.

Subjects will contribute AEs and weeks at risk to each analysis period for as long as they are on the corresponding study treatment in that analysis period. Thus, if they progress from T cell depletion to darTreg infusion at any dose, they will contribute subsequent AEs and weeks at risk to the darTreg infusion analysis period when they initiate any darTreg infusion and that will continue until the end of their follow-up time on study.

In addition, a third subset of the safety sample will include any enrolled subject who has PBMCs collected for darTreg manufacturing (phlebotomy or leukapheresis) and may or may not receive subsequent Thymoglobulin®, darTreg supportive IS or darTreg infusions.

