# 15.6 Sample Size Considerations

This pilot study is designed to evaluate 18 subjects through Stage 3 in a modified 3+3 dose escalation design. Therefore, no formal power and sample size analyses have been performed. However, with 18 evaluable subjects undergoing darTreg supportive IS for 12 weeks of follow-up (6 subjects for 40 weeks of follow-up) and up to 12 evaluable subjects undergoing darTreg infusions for 28 weeks of follow-up after infusion, exact 95% confidence intervals on person-week incidence rates will vary in width by analysis period. For example, the following table (*Table 8. Incidence Rates and Confidence Intervals for Selected Numbers of Events and Person-Weeks*) shows incidence rates and confidence intervals for selected numbers of events and person-weeks of 216 (18 subjects x 12 weeks), 336 (12 subjects x 28 weeks), and 384 (6 subjects x 40 weeks + 12 subjects x 12 weeks) in the two analysis periods. It is not known at this time how many subjects may be expected to comprise the entire Safety Sample, which includes subjects who only received leukapheresis.

Confidential Page 65 of 80

Table 8. Incidence Rates and Confidence Intervals for Selected Numbers of Events and Person-Weeks

Number of	Total Person-	Person-Weeks	Lower 95%	Upper 95% Confidence
Events	Weeks	Incidence Rate	Confidence Limit	Limit
2	216	0.0093	0.0011	0.0334
4	216	0.0185	0.0050	0.0474
6	216	0.0278	0.0102	0.0605
8	216	0.0370	0.0160	0.0730
10	216	0.0463	0.0222	0.0851
12	216	0.0556	0.0287	0.0970
14	216	0.0648	0.0354	0.1087
16	216	0.0741	0.0423	0.1203
18	216	0.0833	0.0494	0.1317
20	216	0.0926	0.0566	0.1430
2	336	0.0060	0.0007	0.0215
4	336	0.0119	0.0032	0.0305
6	336	0.0179	0.0066	0.0389
8	336	0.0238	0.0103	0.0469
10	336	0.0298	0.0143	0.0547
12	336	0.0357	0.0185	0.0624
14	336	0.0417	0.0228	0.0699
16	336	0.0476	0.0272	0.0773
18	336	0.0536	0.0317	0.0847
20	336	0.0595	0.0364	0.0919
2	384	0.0052	0.0006	0.0188
4	384	0.0104	0.0028	0.0267
6	384	0.0156	0.0057	0.0340
8	384	0.0208	0.0090	0.0410
10	384	0.0260	0.0125	0.0479
12	384	0.0313	0.0161	0.0546
14	384	0.0365	0.0199	0.0612
16	384	0.0417	0.0238	0.0677
18	384	0.0469	0.0278	0.0741
20	384	0.0521	0.0318	0.0804

Confidential Page 66 of 80

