PBMC Collection Visit does not apply to Cohort 1. Cohort 2 can have whole blood collection for PBMC isolation if hemoglobin is ≥10.5 mg/dl; leukapheresis if <10.5 mg/dl.

<sup>2 Screening for eligibility C1 and C2 can be assessed between 5-6 weeks (30-44 days) after transplantation. Everolimus can be started on or after 30 days after liver transplantation if eligibility criteria are met (Screen C1).

 $^3\mbox{HIV/HBV/HCV}$  serology can be within one year of screening.

<sup>4AFP is only required for subjects known to have HCC. At Screen A, AFP should be drawn if unavailable within 3 preceding months; AFP should be redrawn at time of transplant. After transplant, AFP should be recorded every 3 months.

<sup>5 First EVR level should be obtained within one week of first dose (+/- 2 days). MMF discontinuation and TAC trough 3-5 μg/L for subjects converting to EVR only. Subjects continuing on TAC-based IS should have troughs 6-8 μg/L.

<sup>6 Prior to Thymoglobulin, collect AE's/SAE's occurring within 72 hours after PBMC Collection only. Collect all AE's/SAE's grade 2 and higher from the time of first Thymoglobulin infusion.

<sup>7 Central laboratory assessments may be drawn up to one year BEFORE solumedrol dose in OR. Once drawn, mechanistic labs do not need to be repeated.

<sup>8CBC, Basic Chemistry, Liver Function Tests, and PT/INR/PTT should be collected as close to, but prior to transplant as possible.

<sup>9Liver allograft biopsy should be obtained prior to transplantation (back table) for local pathology reading only, no specimen for central pathology

<sup>10 Screening should take place within 24 hours prior to Thymoglobulin®. The first dose of Thymoglobulin® is to be given within 72 hours after transplantation. Additional doses of 0.75-1.5 mg/kg IV will be administered until CD3 count is ≤50 cells/μL (50 cells/mcL) or total lymphocyte count is ≤ 0.10 x 10 ½L; or when maximum dose of 4.5/mg/kg has been given. Day 2 and Day 6 visits are only needed if Thymoglobulin is given on these days.

 Treg expansion should be initiated 2-3 weeks prior to planned Treg infusion if subjects continue to meet eligibility criteria. Please refer to Stage 3 Schedule of Events. .

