5. ANALYSIS SAMPLES

The Safety Sample will be comprised of all study subjects who are consented and receive any study therapy, including leukapheresis, Treg-supportive IS and darTreg infusion. This excludes consented subjects who were terminated before receiving any study treatment.

Safety and clinical outcomes will be analyzed within the Safety Sample as a whole and within the following two treatment-related analysis periods during which:

- Subjects receive any darTreg supportive IS
- Subjects receive darTreg infusions at any dose.

Subjects will contribute adverse events and weeks at risk to each analysis period for as long as they are on the corresponding study treatment in that analysis period. Thus, if they progress from darTreg supportive IS to darTreg infusions at any dose, they will contribute subsequent adverse events and weeks at risk to the darTreg infusion analysis period when they initiate any darTreg infusion and that will continue until the end of their follow-up time on study.

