9.2 Adverse Events

All adverse events will be classified by system organ class and preferred term, according to a standardized thesaurus (MedDRA version 17.0). The severity of AEs will be classified using the National Cancer Institute's Common Toxicity Criteria for Adverse Events, with the exception of infections which will be graded according to protocol definitions.

An overall summary table will be developed to report the number of events and the number and percentage of subjects having at least one event in the following categories:

- AEs
- AEs indicated as serious (SAEs)
- AEs that lead to study discontinuation
- AEs with an outcome of death
- AEs reported by maximum severity

In addition, adverse events classified by MedDRA system organ class and preferred term will be summarized for each study cohort and overall for each of the following:

- All AEs
- AEs by maximum severity
- AEs by study stage

The summary tables will present the total number of events as well as the number and percentage of subjects experiencing the events. When reporting the number of AEs, if the same AE occurs for a subject on multiple occasions the event will be counted once for each occurrence. When reporting the number of subjects experiencing the events, a subject will only be counted once if they ever experience an event within the particular system organ class or preferred term. Percentages will be based on the number of subjects in the analysis population.

A summary table of incidence rates adverse events classified by system organ class and MedDRA preferred term will be provided. Incidence rate for a system organ class or preferred term will be defined as the number of adverse events divided by the person-time since the subject enrolled.

Separate data listings will be provided for AEs leading to study discontinuation.

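### The SAP's Safety Sample counts subjects who only had cells collected, which can lower by-cohort percentages of post-transplant events in Cohorts 2-4 against Cohort 1, and whole-sample proportions

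*SAP*

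**What the plan says.** SAP 5 (Analysis Samples) defines the Safety Sample as "all study subjects who are consented and receive any study therapy, including leukapheresis, Treg-supportive IS and darTreg infusion". Protocol 15.6 confirms the consequence: the sample is one "which includes subjects who only received leukapheresis", and its size is stated to be unknown.

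SAP 8.1 runs every analysis on this population, and SAP 9.1 makes it the default for safety. In SAP 9.2, AEs by system organ class and preferred term "will be summarized for each study cohort and overall for each of the following", and "Percentages will be based on the number of subjects in the analysis population". SAP 9.3 treats serious AEs in the same way. SAP 8.1.1 reports the five named safety outcomes for the whole Safety Sample and within two treatment-related periods (supportive IS, and darTreg infusion). It states no split by cohort.

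In the protocol, Appendix 1 notes that "PBMC Collection Visit does not apply to Cohort 1". Section 10.1 says that "collection of AEs and SAEs in Stage 1 are limited to events occurring within 72 hours after leukapheresis"; section 14.4.1 adds later events that the investigator thinks may be linked to the collection. Under section 13.4.1, subjects who leave in Stage 1, or who discontinue before study Thymoglobulin, are not followed. Section 15.4.1 also states that "a third subset of the safety sample will include any enrolled subject who has PBMCs collected for darTreg manufacturing". SAP 5 has no such subset.

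**The concern.** A subject whose only study exposure was cell collection cannot appear in a numerator for rejection, transplant wound complications or darTreg reactions. No post-transplant event in that subject would be collected. Counting the subject in the denominator lowers the percentage without adding information.

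The effect is uneven. Only Cohorts 2-4 have a collection visit, so only they can carry collection-only members. Protocol 13.3 replaces subjects who fail Screen B (the eligibility check before Thymoglobulin), so these denominators can grow while the treated number stays fixed. The by-cohort tables in SAP 9.2 and 9.3 are where a reader would set the dose cohorts beside the IS-only cohort. For post-transplant events the distortion there runs in one direction, towards making the darTreg cohorts look safer. With 3 to 6 treated subjects planned per cohort, each extra member of the denominator is visible.

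**Working it through.** **The plan's own figures.** SAP Table 1 uses 18 × 12 = 216, 12 × 28 = 336 and 6 × 40 + 12 × 12 = 384 person-weeks. All 30 rows reproduce with exact Poisson limits; for example, 2/216 = 0.0093 (0.0011, 0.0334). These denominators contain treated subjects only, so the table is silent on the effect of collection-only subjects.

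**Inputs.**
- Infused: 12 in all (SAP 3), of whom 6 in Cohort 4. Cohort 1: 6, never infused.
- Attrition, protocol 4.4: "we aim to enroll a minimum of 6-8 patients per year to ensure that 4-5 will progress to darTreg infusion". Enrolled per infused ranges from 6/5 = 1.2 to 8/4 = 2.0. Pairing low with low and high with high gives 6/4 = 1.5 and 8/5 = 1.6.
- Number of collection-only subjects: not given. Lower bound: none. Upper bound (assumption): the 2.0 ratio, with every loss occurring after collection and before Thymoglobulin.

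**Cohort 4 in the SAP 9.2/9.3 tables.** Denominator = 6 × ratio if all losses are collection-only: 6 × 1.2 = 7.2; 6 × 1.5 = 9; 6 × 1.6 = 9.6; 6 × 2.0 = 12. With no collection-only subjects it is 6.

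| Denominator | 1 event | 2 events |
|---|---|---|
| 6 (no dilution) | 16.7% | 33.3% |
| 9 | 11.1% | 22.2% |
| 12 (upper bound) | 8.3% | 16.7% |

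Cohort 1, with 2 events in 6, stays at 33.3% in every row.

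**Whole sample in SAP 8.1.1**, reading a proportion as subjects with the event over subjects, with exact binomial limits. At the upper bound 12 infused need 12 × 2.0 = 24 enrolled, so 12 are collection-only and the sample is 6 + 24 = 30.
- Rejection, 4 subjects: 4/18 = 22.2% (6.4-47.6); 4/30 = 13.3% (3.8-30.7).
- darTreg-attributable events, 2 subjects: 2/12 infused = 16.7% (2.1-48.4); 2/18 once Cohort 1 is added = 11.1% (1.4-34.7); 2/30 = 6.7% (0.8-22.1). The step from 12 to 18 comes from Cohort 1, not from collection-only subjects.

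**Person-week rates.** If each collection-only subject contributes only the 72-hour window (assumption), 12 × 3/7 = 5.1 weeks are added to 18 × 40 = 720, about 0.7%. This does not carry over to the incidence-rate table in SAP 9.2, which counts person-time from enrolment and so can include waiting-list time.

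**Start of the IS period.** Protocol 15.4.1 starts it with any Thymoglobulin; SAP 5 starts it with any supportive IS. Protocol 6.1.3 starts MMF within 24 hours of transplant, and 6.1.2 starts tacrolimus within 72 hours. Screen B includes ICU status at 72 hours (4.3.2). A subject of any cohort could thus begin these drugs, fail Screen B, and be read into the SAP's IS period, although Stage 2 AE collection begins only at first Thymoglobulin (14.4.1).

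**The case against.** A reader might infer that all results for rejection, wound complications and darTreg reactions are diluted and cannot be compared between cohorts. The documents do not support that. SAP 5 and 8.1.1 also analyse the five named outcomes within two treatment periods, to which collection-only subjects add neither events nor weeks at risk. SAP 8.1.1 plans no cohort split for those outcomes. Comparing darTreg-attributable events with Cohort 1 has no meaning in any case, since Cohort 1 is not infused.

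A reader might also infer that the plan implies 7 to 12 subjects in Cohort 4's denominator. It does not. Protocol 4.4 states an annual aim within one center's recruitment discussion and expects attrition at each phase. Losses before collection never enter the Safety Sample. Losses after Thymoglobulin are exposed subjects who belong in a Thymoglobulin denominator. If, say, 3 of 6 losses came after Thymoglobulin, the correct comparison for one event would be 1/9 = 11.1% against 1/12 = 8.3%.

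The consequence is also limited. The analyses are descriptive, the stopping rules in protocol 14.8.1 use absolute counts, and SAP 8.1.1 and 9.2 report counts beside the percentages. SAP 5.1 tabulates screen failures by stage and cohort, so an attentive reader could reconstruct who was treated. Under the broad reading of supportive IS, Cohort 1 could itself contain Screen B failures.

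All of this stands and narrows the point. It does not remove it: the by-cohort tables and the whole-sample proportions are still planned, and their stated denominator still includes subjects who could not have the event.

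**Conclusion.** The point holds for two sets of results: the by-cohort AE and serious AE percentages in SAP 9.2 and 9.3, and the whole-sample proportions in SAP 8.1.1. For events arising after transplant, collection-only subjects can only lower these figures, and between cohorts they lower only Cohorts 2-4. AEs of the collection itself are different, because these subjects can supply the numerator. The treatment-period analyses are not diluted by these subjects, and the stopping rules are unaffected.

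The size is unknown. It runs from no effect to a halving in Cohort 4 (one event: 16.7% down to 8.3%). The halving rests on the most unfavourable attrition ratio in protocol 4.4 and on every loss being collection-only. For darTreg-attributable events in the whole sample, adding Cohort 1 alone reduces the proportion by a third (12 becomes 18). The change is worth making because safety is the trial's main purpose and the correction costs almost nothing.

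**What to change.** Set denominators by exposure in SAP 8.1.1, 9.2 and 9.3:
- **Collection AEs:** the protocol 15.4.1 collection subset, restored to SAP 5 and worded to cover both leukapheresis and whole-blood collection.
- **Rejection, infection, wound complications and cytopenias, and the by-cohort AE and serious AE tables:** subjects given any Thymoglobulin.
- **darTreg-attributable AEs:** subjects given any part of a darTreg infusion.

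In SAP 5, start the IS period at any Thymoglobulin, as protocol 15.4.1 does.

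The cost is SAP wording. No new data are needed, and the reported percentages become slightly less favourable.

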5.1 Screen Failure Analysis

At each stage of the study, subject's eligibility will be re-evaluated. Reasons for study discontinuation for screen failures will be summarized at each stage, both overall and within each cohort.

6. DEMOGRAPHIC AND OTHER BASELINE CHARACTERISTICS

Summary descriptive statistics for baseline and demographic characteristics will be provided for all enrolled participants. Demographic data will include age, race, sex, body weight, and height; these data will be presented in the following manner:

- Continuous data (i.e., age, body weight, and height) will be summarized descriptively by mean standard deviation, median, and range.
- Categorical data (i.e., sex and race) will be presented as enumerations and percentages.

Both Recipient and Donor demographic and baseline characteristic data will also be presented in data listings by subject.

7. INTERIM ANALYSES AND DATA MONITORING

There are no interim analyses planned for this study.

The protocol chair, the ITN clinical trial physician, the NIAID medical monitor, and the NIAID Transplant Data and Safety Monitoring Board (DSMB) will periodically review safety data. Enrollment of subjects in the trial and/or potentially progression from one stage of the trial to the subsequent stage for current trial subjects may be suspended at any time if any of these reviews concludes that there are significant safety concerns. Stopping rules are described in Section 18.3.1 of the protocol.

The progress of the study will be monitored by the NIAID Transplant DSMB. The DSMB will be chartered to review safety data and to make recommendations regarding continuation, termination, or modification of the study. The DSMB will formally review the safety data at least yearly. The discontinuation of study treatment will also be periodically reported to the DSMB.

In addition, safety data will be reviewed by the DSMB when an event occurs that is of sufficient concern to the NIAID medical monitor or protocol co-chairs to warrant review, or when an event occurs that could contribute to a pre-defined stopping rule as specified in the Protocol.

Findings will be reported to IRBs and health authorities.

